3.1 Sample size calculation

Sample size calculations are described in the protocol section 17.1 and will not further be described here.

3.2 Definition of analysis sets

The following analysis sets are defined in accordance with the ICH-E9 guidance.ⁱⁱⁱ

- **Full Analysis Set (FAS):** includes all randomised subjects. The statistical evaluation of the FAS will follow the intention-to-treat (ITT) principle and subjects will contribute to the evaluation “as randomised”.
- **Safety Analysis Set (SAS):** includes all subjects receiving at least one dose of liraglutide. Subjects in the safety analysis set will contribute to the evaluation “as treated”.

Subjects who are lost to follow up and where no exposure information of liraglutide is available will be handled as unexposed.

3.3 Primary endpoint

The primary endpoint is the change from baseline in HbA1c after 26 weeks of treatment.

The change from baseline in HbA1c after 26 weeks of treatment will be analysed using an analysis of covariance (ANCOVA) model with treatment as a fixed effect and baseline HbA1c as a covariate.

Missing values after 26 weeks of treatment will be imputed applying last observation carried forward (LOCF) using HbA1c values at and after baseline.

Superiority of liraglutide 1.8 mg/day vs. liraglutide 0.9 mg/day will be considered as confirmed if the 95% confidence interval for the treatment difference (liraglutide 1.8 mg/day minus liraglutide 0.9 mg/day) for change from baseline in HbA1c lies entirely below 0.0%; equivalent to a one-sided test with significance level of 2.5%. Conclusion of superiority will be based on FAS.

Additionally, change from baseline in HbA1c after 52 weeks of treatment will be presented descriptively for the liraglutide 1.8 mg/day treatment arm.

Sensitivity analysis

Sensitivity analysis will be performed on FAS using the mixed model for repeated measurements (MMRM) method. All HbA1c values available post baseline at scheduled measurement times will be analysed in a linear mixed normal model using an unstructured residual covariance matrix for HbA1c measurements within the same subject. The model will include treatment and visit as fixed factors and baseline HbA1c as a covariate. Interactions between visit and treatment and between

visit and baseline HbA1c will also be included in the model. The results of sensitivity analyses will be compared to the result of the standard ANCOVA method using LOCF for imputation of missing data.

Further, a pattern mixture model approach using multiple imputation and mimicking an ITT scenario will be applied. Imputation in both arms will be based on liraglutide 0.9 mg/day values. The imputations will be done as follows:

- In the first step, for each subject with a non-monotone missing data pattern, missing values at visits prior to the last non-missing value for that subject are imputed using a Markov Chain Monte Carlo (MCMC) method (with seed of 20170427), in order to obtain a monotone missing data pattern. This imputation is done for each treatment group separately and 1000 copies of the dataset will be generated.
- In the second step, for each of the 1000 copies of the dataset, an analysis of variance model with baseline HbA1c as a covariate is fitted to the change in HbA1c from baseline to 4 weeks (Visit 11) for liraglutide 0.9 mg/day only. The estimated parameter and their variance from this model are used to impute missing values at 4 weeks for subjects in both the liraglutide 0.9 mg/day and liraglutide 1.8 mg/day groups, based on HbA1c at baseline.
- In the third step, for each of the 1000 copies of the dataset, missing HbA1c values at 8 weeks (Visit 12) are imputed in the same way as for 4 weeks. Now the imputations are based on an analysis of variance model with the HbA1c values at baseline and 4 weeks as covariates, fitted to liraglutide 0.9 mg/day group.
- This stepwise procedure is then repeated sequentially over the available planned visits, adding one visit in each step until 26 weeks (Visit 16). In this stepwise procedure, seed of 19671230 will be used.
- For each of the complete data sets, the change from baseline to 26 weeks is analysed using an analysis of covariance model with treatment as a fixed effect and baseline HbA1c value as a covariate.

The estimates and standard deviations for the 1000 data sets are pooled to one estimate and associated standard deviation using Rubin's rule^{iv}. From these pooled estimates the confidence interval for the treatment differences and the associated p-value are calculated.

3.4 Secondary endpoints

3.4.1 Efficacy endpoints

Endpoints evaluated after 26 weeks of treatment

In the statistical analysis for the responder endpoints, the endpoint derived from imputed HbA1c and/or body weight by LOCF will be used.

Responder for HbA1c

Two dichotomous endpoints (responder/non-responder) will be defined based on whether a subject has met a specific target level after 26 weeks of treatment:

- HbA1c target < 7.0%^y
- HbA1c target \leq 6.5%^{vi, vii}

Analysis of each of the two responder endpoints will be based on a logistic regression model with treatment as factor and baseline HbA1c value as a covariate.

HbA1c responder endpoints without weight gain

Responder for HbA1c without weight gain after 26 weeks of treatment will be defined as HbA1c < 7.0% after 26 weeks of treatment and change from baseline in body weight after 26 weeks of treatment below or equal to zero. Analysis will be based on a logistic regression model with treatment as factor and baseline HbA1c and baseline body weight values as covariates.

HbA1c responder endpoints without treatment emergent severe or blood glucose (BG) confirmed symptomatic hypoglycaemic episodes

Responder for HbA1c without hypoglycaemic episodes after 26 weeks of treatment will be defined as HbA1c < 7.0% after 26 weeks of treatment and without severe or BG confirmed symptomatic episodes during 26 weeks of treatment. Analysis will be based on a logistic regression model with treatment as factor and baseline HbA1c values as a covariate.

Fasting plasma glucose (FPG)

Change from baseline in FPG after 26 weeks of treatment will be analysed using the standard ANCOVA model.

Waist circumference

Change from baseline in waist circumference after 26 weeks of treatment will be analysed using the standard ANCOVA model.

Body weight

Change from baseline in body weight after 26 weeks of treatment will be analysed using the standard ANCOVA model.

Body Mass Index (BMI)

Change from baseline in BMI after 26 weeks of treatment will be analysed using the standard ANCOVA model.

Self measured blood glucose (SMBG) 7-point profile

Three endpoints from the 7 point SMBG profile will be defined:

- 7-point profile (individual points in the profile)
- Mean of the 7-point profile, defined as the area under the profile (calculated using the trapezoidal method) divided by the measurement time. The area under the profile will be calculated for profiles which have at least one valid measurement. If a profile has only one valid measurement (e.g. 170 mg/dL before lunch), the value (i.e. 170 mg/dL) is set to the mean of 7-point profile.
- Mean of postprandial increments (from before meal to 90 min after for breakfast, lunch and dinner). The mean increment over all meals will be derived as the mean of all available meal increments. In case of only one valid increment (eg. 50 mg/dL for breakfast), the increment (i.e. 50 mg/dL) is set to the mean of postprandial increments.

A linear mixed effect model will be fitted to the 7-point SMBG profile data. The model will include treatment, time and interaction between treatment and time as fixed factors and subject as random effect. From the model mean profile by treatment and relevant treatment differences will be estimated and explored.

Change from baseline after 26 weeks of treatment in mean of the 7-point profile and post-prandial increment endpoints will be analysed separately using the standard ANCOVA model.

Blood pressure (systolic and diastolic)

Change from baseline in systolic blood pressure and diastolic blood pressure after 26 weeks of treatment will be analysed separately using the standard ANCOVA model.

Fasting C-peptide, fasting insulin, fasting glucagon, proinsulin, proinsulin/insulin, HOMA-B, HOMA-IR

In addition to fasting C-peptide, fasting insulin, fasting glucagon, and proinsulin, three derived parameters will be calculated; proinsulin/insulin ratio, beta-cell function (HOMA-B) and insulin resistance (HOMA-IR).

The calculation of the HOMA endpoints will be done as follows:

- Beta-cell function (%) = $20 \cdot \text{fasting insulin} [\mu\text{U/mL}] / (\text{FPG} [\text{mmol/L}] - 3.5)$
- Insulin resistance (%) = $\text{fasting insulin} [\mu\text{U/ml}] \cdot \text{FPG} [\text{mmol/l}] / 22.5$

These endpoints after 26 weeks of treatment will be analysed separately using the standard ANCOVA model. In these statistical analyses the endpoint will be log-transformed and so will the baseline covariate.

Fasting lipid profile

Total cholesterol, low density lipoprotein cholesterol (LDL cholesterol), high density lipoprotein cholesterol (HDL cholesterol), very low density lipoprotein cholesterol (VLDL cholesterol), triglycerides, and free fatty acids after 26 weeks of treatment will be analysed separately by using the standard ANCOVA model. In these statistical analyses the endpoint will be log-transformed and so will the baseline covariate.

Endpoints evaluated after 52 weeks of treatment

All above listed efficacy endpoints will be summarised descriptively for the liraglutide 1.8 mg/day arm after 52 weeks of treatment.

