Unless otherwise specified, laboratory values below the lower limit of quantification (LLOQ) will be set to $\frac{1}{2}$ LLOQ.

For measurements over time, mean values will be plotted to explore the trajectory over time. LOCF imputed data will be used as the basis for plotting data, if not otherwise specified. For endpoints that are analysed log-transformed, the geometric mean values will be plotted.

An analysis of covariance (ANCOVA) model will be applied for the primary endpoint and continuous secondary endpoints after 26 weeks of treatment. The model includes treatment as a fixed effect and the corresponding baseline value as a covariate. In the following, this model will be referred to as the standard ANCOVA model.

Presentation of results from a statistical analysis will include the estimated mean treatment effects (Least Square Means [LSMeans]) for absolute values and change from baseline. In addition, estimated mean treatment difference (or ratio) will be presented together with the two-sided 95% confidence interval and corresponding two-sided p-value. The “obsmargins” option will be used in the “LSMEANS TREATMENT”.ⁱ

Handling of missing data

The expected percentage of missing data is around 10%. In accordance with industry guidanceⁱⁱ endpoints will be assessed at frequent visits and also on subjects who withdraw prematurely. This will facilitate an analysis in accordance with ITT principles. Also, the combined information on frequent outcomes and information on reason for drop-out is assumed to account for the missing data anticipated.

If not otherwise specified, the value from the randomisation visit (Visit 8) will be used as the baseline value. If the value measured at the randomisation visit is missing and the assessment has also been made at an earlier visit, then the non-missing value obtained at the preceding visit closest to Visit 8 will be used as the baseline value.

Missing values (including intermittent missing values) will be imputed using the LOCF method. Subjects without data after randomisation will be included by carrying forward their baseline value. In this trial, sensitivity analyses will be made to examine the robustness of the LOCF method.

Handling of laboratory measurements

A laboratory measurement in which the central laboratory could not guarantee a reliability of data, e.g. measurements with a comment like "Only for reference because of xxxx", will not be used for the summary and statistical analysis.

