- Asymptomatic hypoglycaemia: An episode not accompanied by typical symptoms of hypoglycaemia, but with a measured plasma glucose concentration ≤ 3.9 mmol/L (70 mg/dL).
- Documented symptomatic hypoglycaemia: An episode during which typical symptoms of hypoglycaemia are accompanied by a measured plasma glucose concentration ≤ 3.9 mmol/L (70 mg/dL).
- Pseudo-hypoglycaemia: An episode during which the person with diabetes reports any of the typical symptoms of hypoglycaemia with a measured plasma glucose concentration > 3.9 mmol/L (70 mg/dL) but approaching that level.
- Probable symptomatic hypoglycaemia: An episode during which symptoms of hypoglycaemia are not accompanied by a plasma glucose determination but that was presumably caused by a plasma glucose concentration ≤ 3.9 mmol/L (70 mg/dL).

Note: Glucose measurements are performed with capillary blood calibrated to plasma equivalent glucose values

Figure 3-2 ADA classification of hypoglycaemia

Hypoglycaemic episodes will be summarised descriptively for each of the following periods separately:

- The run-in period: Treatment emergent hypoglycaemic episodes where the onset date of the episode occurs on or after the first day of exposure to liraglutide and before the date of randomisation will be reported as part of the run-in period. For the run-in failure subjects, hypoglycaemic episodes where the onset date of the episode occurs on or after the first day of exposure to liraglutide and no later than seven days after the last day of liraglutide treatment will be reported as part of the run-in period.
- The 26 week treatment period: Treatment emergent hypoglycaemic episodes where the onset date of the episode occurs on or after the date of randomisation and no later than seven days after Visit 16 (EOT26) will be reported as during 26 weeks of treatment. For subjects in the liraglutide 0.9 mg arm as well as for subjects in both arms who withdrew from the trial during 26 weeks of treatment, treatment emergent hypoglycaemic episodes with an onset date on or after the date of randomisation and no later than seven days after the last day of liraglutide treatment will be reported as part of 26 weeks of treatment.
- The 52 week treatment period: For the liraglutide 1.8 mg arm all treatment emergent hypoglycaemic episodes with an onset date on or after the date of randomisation will be reported as during 52 weeks of treatment.

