For each of the periods listed above, data on hypoglycaemic episodes are presented above in terms of the number of subjects with at least one event (N), the percentage of subjects with at least one event (%), the number of events (E) and the event rate per 100 years (R). Separate summaries are made for severe or BG confirmed symptomatic hypoglycaemic episodes, nocturnal severe or BG confirmed symptomatic hypoglycaemic episodes and the ADA classification of hypoglycaemia.

The number of hypoglycaemic episodes during 26 weeks of treatment will be analysed separately for each endpoint listed above using a negative binominal regression model with a log-link function and the logarithm of the time period in which a hypoglycaemic episode is considered to be part of the 26 week treatment period as offset. The model will include treatment as factor. For each endpoint, the analysis will be performed only if the number of episodes observed is adequate for convergence of the model fit.

Pulse

Pulse will be summarized descriptively.

Clinical evaluations (physical examination, eye examination and ECG)

Eye examination (fundoscopy/fundus photography) and ECG findings will be summarised descriptively, including:

- summaries for each visit
- shift table from baseline to after 26 weeks of treatment and after 52 weeks of treatment

Any findings in the physical examination evaluation at screening will be presented as listings. Any clinically significant deterioration of a pre-existing condition after the screening visit, as well as any new clinically significant findings will be recorded as adverse events.

Laboratory assessments

All laboratory parameters will be summarised descriptively.

The following tables will be presented based on both observed and LOCF imputed data:

- Shift tables from baseline to after 26 weeks of treatment and after 52 weeks of treatment
- Proportion of subjects with measurements outside reference range by treatment and week.

Laboratory values will be presented graphically as box plots by treatment and week.

For each laboratory parameter, individual values outside the reference ranges (abnormal values) will be listed.

For lipase and amylase the following rule will apply in the evaluation of the result:

- If the amylase or lipase baseline (at screening) value is $> 3 \times \text{UNR}$ this information is to be recorded as medical history for that subject.

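### In the hypoglycaemia-free HbA1c responder endpoint, weeks after withdrawal are scored as episode-free, and no sensitivity analysis covers this

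*SAP*

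**What the plan says.** SAP section 3.4.1 sets one missing-data rule for all responder endpoints: "In the statistical analysis for the responder endpoints, the endpoint derived from imputed HbA1c and/or body weight by LOCF will be used". Two of these endpoints are composites.

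- **Hypoglycaemia composite:** "HbA1c < 7.0% after 26 weeks of treatment and without severe or BG confirmed symptomatic episodes during 26 weeks of treatment". It is analysed by logistic regression on treatment and baseline HbA1c.
- **Weight composite:** HbA1c below 7.0% together with "change from baseline in body weight after 26 weeks of treatment below or equal to zero". Baseline body weight is added as a covariate.

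Section 3.4.1 has no rule for a subject who was not followed for 26 weeks. The endpoint counts treatment emergent episodes, so the periods defined in section 3.4.2 apply. For a subject who withdrew, episodes with onset "no later than seven days after the last day of liraglutide treatment will be reported as part of 26 weeks of treatment".

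The negative binomial model for the number of episodes, also in section 3.4.2, uses "the logarithm of the time period in which a hypoglycaemic episode is considered to be part of the 26 week treatment period as offset".

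Under Handling of missing data, section 3 adds: "Subjects without data after randomisation will be included by carrying forward their baseline value". It also states: "The expected percentage of missing data is around 10" per cent, with no split by arm. The same text announces sensitivity analyses of LOCF. Section 3.3 specifies them (MMRM and a pattern mixture model) for change in HbA1c only.

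**The concern.** LOCF can carry forward a good or a bad HbA1c. The hypoglycaemia component works differently: once the window has closed, no later episode can turn the subject into a failure. Being unobserved therefore counts as success on that component, and the subject is reported as free of episodes over 26 weeks that were not all observed.

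The SAP corrects for short observation when it models episode counts but not when it uses the same episodes in the responder endpoint. Both composites are marked in section 2.2.1 as key secondary endpoints for disclosure, so the proportions and odds ratios will be published. As the plan stands, no analysis would show how far they rest on unobserved time.

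**Working it through.** The SAP gives no responder rate or episode risk and refers to the protocol for sample size, so there is no planned figure to reproduce. The check traces the rule and then sizes it.

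**Tracing the rule.** Take a subject who withdraws at week 5 with no episode and a last HbA1c below 7.0%.

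1. Under Visit reallocation in section 3, the premature-discontinuation value fills an adjacent missing visit, here week 4 or week 8.
2. LOCF carries it to week 26, so the HbA1c criterion is met.
3. The episode window closes seven days after the last dose, so the hypoglycaemia criterion is met.
4. The subject is a 26-week responder.

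In the weight composite, the last observed weight is carried forward, so a subject who had gained weight stays a failure. A change of exactly zero is automatic only with no post-randomisation weight. A subject with no post-randomisation data at all would also need a baseline HbA1c below 7.0%.

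**Inputs.** From the SAP: d = 10% missing, treated here as drop-out. All others are assumptions:

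- R = 0.40, share of completers with HbA1c below 7.0%
- q = 0 to 0.60, share of drop-outs whose carried-forward HbA1c is below 7.0%
- h = 1% to 20%, 26-week risk of at least one episode, at a constant rate and independent of HbA1c
- f = 0.25, fraction of the 26 weeks observed in drop-outs
- 15% versus 5% drop-out for the comparison of arms

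**Composite rate under the SAP:** (1−d)·R·(1−h) + d·q·(1−h)^f.

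With d = 0.10, q = 0.40, h = 5%, and 0.95^0.25 = 0.987:

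- SAP rule: 0.90×0.40×0.95 + 0.10×0.40×0.987 = 0.3420 + 0.0395 = 38.15%
- Episode risk extended to 26 weeks: 0.3420 + 0.10×0.40×0.95 = 38.00%
- Drop-outs as non-responders: 34.20%

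**Credit for unobserved time alone:** d·q·[(1−h)^f − (1−h)].

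- q = 0.40, h = 5%: 0.04×(0.987−0.950) = 0.15 points
- q = 0.60, h = 20%: 0.06×(0.946−0.800) = 0.87 points
- q = 0: 0 points

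The credit is never negative. Even with f = 0 its ceiling would be 0.10×0.60×0.20 = 1.2 points, so the choice of f matters little.

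**All drop-outs credited as responders,** against counting them as non-responders: d·q·(1−h)^f, which is 0 at q = 0 and 0.10×0.60×0.9975 = 6.0 points at q = 0.60, h = 1%.

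**Gap between arms with no true difference,** high minus low drop-out: (0.15−0.05)·[q(1−h)^f − R(1−h)]. At h = 5%:

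| q | Gap (points) |
|---|---|
| 0 | −3.8 |
| 0.15 | −2.3 |
| 0.20 | −1.8 |
| 0.40 | +0.15 |
| 0.50 | +1.1 |
| 0.60 | +2.1 |

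The sign changes at q = 0.38/0.987 = 0.385. If drop-outs are counted as non-responders, the gap is −0.10×0.38 = −3.8 points at every q.

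**The case against.** The strongest reply is that the part specific to hypoglycaemia is small. It is below 1 point at 10% drop-out under these assumptions; most of the responders credited without full follow-up come from ordinary LOCF of HbA1c. This stands, and it limits the size of the point.

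Counting drop-outs as non-responders is not neutral either. With unequal drop-out it moves the result by 3.8 points against the arm that loses more subjects, at least as much as the SAP rule at every q examined for h = 5%. This also stands: the choice is one of estimand, so the second analysis belongs beside LOCF and should not replace it.

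Section 3 plans to assess subjects who withdraw, and section 3.4.2 gives an exposure-adjusted episode analysis. The first may recover some week-26 HbA1c values but does not reopen the episode window. The second answers a different question and leaves the composite unchanged.

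A reader might go further than the SAP allows in three ways:

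- **The rule favours the arm with more drop-out.** This is true of the hypoglycaemia component alone, or in comparison with non-responder counting. The whole composite can move either way.
- **Drop-out of 15% versus 5%, with 20% to 50% of drop-outs below 7.0%, creates a spurious difference of 2 to 5 points.** That product, 0.10 × 0.2 to 0.5, ignores the completers whom the drop-outs replace. The gap is −1.8 to +1.1 points at R = 0.40 and h = 5%.
- **Drop-outs are generally credited with no weight gain.** They are not, because a carried-forward gain remains a failure. Whether anyone could be randomised with HbA1c below 7.0% depends on eligibility criteria that the SAP does not give.

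**Conclusion.** The point holds in a limited form. In the hypoglycaemia composite, sections 3.4.1 and 3.4.2 together score unobserved weeks as episode-free, without exposure adjustment, a stated rule for incomplete follow-up or a sensitivity analysis. The weight composite shares the LOCF dependence and the missing sensitivity analysis, but the automatic pass is confined to subjects with no post-randomisation weight.

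The credit for unobserved time is 0 to about 0.9 points at 10% drop-out and always favours shorter observation. The net effect on the composite has no fixed sign. The SAP gives no drop-out by arm, so it does not show which arm would gain. Apart from the 10%, every rate used here is an assumption.

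Superiority rests on change in HbA1c (section 3.3), so the primary conclusion is unaffected. The change is still worth making because both composites will be disclosed and the cost is small.

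**What to change.** In section 3.4.1, for both composites:

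1. Add a pre-specified analysis with the same logistic model in which a subject without an observed week-26 HbA1c (and week-26 weight, for the weight composite) is a non-responder. Say whether a premature-discontinuation value reallocated to Visit 16 counts as observed.
2. Report it beside the LOCF analysis.
3. State that episode-free status under LOCF refers only to the time in which episodes were observed. This is needed in any case, because a withdrawn subject whose week-26 HbA1c is recovered still has the shortened episode window.

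The cost is a few lines of SAP text and one extra run. Responder proportions in the added analysis will be somewhat lower. That analysis penalises the arm with more drop-out, so neither version should be read alone; agreement between them is what would reassure.

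### The mixed model for the individual points of the 7-point SMBG profile names no response and, unlike every other efficacy model in the SAP, leaves out baseline, which costs precision

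*SAP*

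**What the plan says.** Section 2.2.1 places the individual points of the SMBG profile, the profile mean and the mean postprandial increment under change from baseline after 26 weeks. All three carry the star that marks endpoints selected for disclosure. Section 3.4.1 treats them under the heading "Endpoints evaluated after 26 weeks of treatment".

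Section 3 sets the general rule for continuous secondary endpoints, the standard ANCOVA: "The model includes treatment as a fixed effect and the corresponding baseline value as a covariate". It also asks for "the estimated mean treatment effects (Least Square Means [LSMeans]) for absolute values and change from baseline", and for treatment differences with 95% intervals and p-values.

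In the SMBG part of Section 3.4.1 that rule is applied to two of the three endpoints: "mean of the 7-point profile and post-prandial increment endpoints will be analysed separately using the standard ANCOVA model". For the individual points the text is: "A linear mixed effect model will be fitted to the 7-point SMBG profile data". The terms follow: "The model will include treatment, time and interaction between treatment and time as fixed factors and subject as random effect". The intended output is: "From the model mean profile by treatment and relevant treatment differences will be estimated and explored".

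**The concern.** Two things are missing from the description of this model.

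- **Baseline.** The listed terms do not include it. This is the only modelled efficacy endpoint in the SAP without a baseline covariate. HbA1c, the four responder analyses, FPG, waist, weight, BMI, the two other SMBG endpoints, blood pressure, the fasting and HOMA parameters and the lipids all have one. The MMRM sensitivity analysis in Section 3.3 has baseline and its interaction with visit. No reason is given for the exception.
- **The response.** Section 2.2.1 points to the change. The mean profile by treatment in Section 3.4.1 points to the week-26 value. Section 3 wants results on both scales. With baseline in the model the choice would not matter for the treatment difference. Without it, the two readings give different differences and different intervals, so two programmers could follow the text and report different results.

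At stake is the precision and the definition of seven treatment comparisons for an endpoint selected for disclosure. Bias is not the issue: with complete data, randomisation protects the expected treatment difference on either reading.

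**Working it through.** **Inputs.** The SAP gives no SMBG standard deviation, no baseline-to-week-26 correlation and no sample size (Section 3.1 refers to the protocol), so it has no figure to reproduce. The width ratios below do not depend on sample size. They depend on the correlation r between baseline and week 26 at the same point, taken here as 0.3, 0.5 and 0.7. Also assumed are an equal variance s² at both visits and complete data.

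**Variance behind each per-point treatment difference, up to the same sample-size factor:**

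- week-26 value, no baseline term: s²
- change, no baseline term: 2s²(1 − r)
- either response, baseline-adjusted: s²(1 − r²)

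**Interval width relative to the adjusted analysis** is the square root of the variance ratio: 1/√(1 − r²) for the value, and √(2/(1 + r)) for the change. The variance ratio itself, 1/(1 − r²) or 2/(1 + r), is the relative number of subjects needed for equal precision.

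| r | Width, value | Width, change | Subjects, value | Subjects, change |
|---|---|---|---|---|
| 0.3 | 1/√0.91 = 1.05 | √(2/1.3) = 1.24 | +10% | +54% |
| 0.5 | 1/√0.75 = 1.15 | √(2/1.5) = 1.15 | +33% | +33% |
| 0.7 | 1/√0.51 = 1.40 | √(2/1.7) = 1.08 | +96% | +18% |

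**Check with the SAP's own model form.** The random-intercept model was fitted by REML to seven points in 600 simulated complete data sets per r. Assumptions: 150 per arm, SD 35 mg/dL, between-point correlation 0.5, true difference −10 mg/dL.

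- Mean estimates lay between −9.88 and −10.15 in all analyses, so none is biased.
- Standard-error ratios to the adjusted model were 1.047, 1.155 and 1.398 (value) and 1.239, 1.152 and 1.083 (change), matching the formulas.

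**Value against change.** Without a baseline term, the two estimates at a point differ by the chance baseline imbalance there. Its standard deviation is s√(2/n) = 35 × √(2/150) = 4.0 mg/dL under the same assumptions (4.1 in the simulation). With the baseline term, subtracting baseline from the response only lowers the baseline slope by 1 and leaves the treatment terms alone. In the simulation the two adjusted fits agreed to within numerical tolerance.

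**Effect of LOCF.** Section 3 expects about 10% missing data. As an extreme case, let all of it be baseline carried forward and ignore mean change. Then r becomes 0.9r + 0.1 = 0.37, 0.55 and 0.73. The width ratios become 1.08, 1.20 and 1.46 (value) and 1.21, 1.14 and 1.08 (change), so the picture is the same.

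**The case against.** The strongest reply is that an unadjusted mixed model is valid, only inefficient. The output is to be explored, the star marks disclosure only, and the one confirmatory claim is on HbA1c. All of that is true and limits the weight of the point. The size of the loss also rests on an assumed r: on the value reading it is only 5% at r = 0.3 and nil at r = 0. On the change reading there is a loss for any r below 1. The unnamed response does not itself widen any interval; it leaves open which estimate is reported.

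Other replies carry less.

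- **The random subject effect already covers baseline.** It does not. Treatment is compared between subjects, and a random intercept on week-26 data models the correlation among the seven points without removing the between-subject variation that baseline predicts.
- **The profile data may include the baseline profiles.** The meaning of time is indeed not defined, and such a fit could give values and changes together. With an unconstrained treatment-by-time term, however, it would still return the unadjusted differences, one for the value and another for the change.
- **The general ANCOVA rule in Section 3 may still apply to the points.** Section 3.4.1 gives them a specific model and names only the two summary endpoints for the standard ANCOVA, so replacement is the more natural reading, though it is not stated.
- **The protocol may name the response.** That cannot be checked here. The SAP itself sets out the model and its terms, and naming the response would not supply the missing covariate.

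**Conclusion.** The point holds. The model for the individual SMBG points has no baseline term and no stated response, and nothing elsewhere in the SAP supplies either. For assumed correlations from 0.3 to 0.7, equal variances and complete data, its intervals are 5% to 40% wider than baseline-adjusted ones if the value is modelled, and 24% down to 8% wider if the change is modelled. The direction is the same for any positive correlation below 1; the size cannot be fixed from the document. The consequence is lost precision and an avoidable choice left open in one exploratory secondary analysis. Section 4 concedes that statisticians and programmers are hard to keep blinded in this design, which is a further reason to settle the response in advance.

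**What to change.** In the SMBG part of Section 3.4.1, replace the model description with wording to this effect:

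> The response is the change from baseline to week 26 at each of the seven points. Fixed effects are treatment, time point (the seven points of the profile), treatment-by-time point, the baseline value at the same time point, and its interaction with time point; subject is a random effect. Mean week-26 profiles by treatment come from the same model by adding the observed mean baseline at each point.

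This matches the form of the MMRM in Section 3.3, and one fit then serves both scales requested in Section 3. Missing week-26 points and missing baselines stay under the general rules there, including the fallback when the randomisation-visit value is absent: "then the non-missing value obtained at the preceding visit closest to Visit 8 will be used as the baseline value".

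The cost is SAP wording and one line of model code, using data already collected. The model gains seven fixed-effect parameters. A subject who still has no baseline at a point after the fallback drops out of that point only.
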